## 1. LIST OF ABBREVIATIONS

**Table 1: Abbreviations and Specialist Terms**

AE	adverse event
AUC	area under the curve
BE	Biomarker Evaluable
BLQ	below the limit of quantitation
BSA	body surface area
C1D1	Cycle 1, Day 1
C2D1	Cycle 2, Day 1
CI	confidence interval
Cmax	maximum drug concentration
CpG	C-phosphate-G (cytosine and guanine separated by only one phosphate)
CR	complete response
CRF	case report form
CT	computerized tomography
CTCAE	Common Terminology Criteria for Adverse Events
DCR	disease control rate
DLT	dose limiting toxicity
DNA	deoxyribonucleic acid
EBV	Epstein-Barr virus
ECG	electrocardiogram
ECOG	Eastern Cooperative Oncology Group
EOT	end of treatment
H-score	measurement of immunoreactivity via IHC
ICF	informed consent form
IP	investigational product
K-M	Kaplan-Meier
MedDRA	Medical Dictionary for Regulatory Activities

MRI	magnetic resonance imaging
NCA	noncompartmental
NCI	National Cancer Institute
NPC	nasopharyngeal carcinoma
ORR	overall response rate
OS	overall survival
PD	pharmacodynamic
PET	positron emission tomography
PFS	Progression free survival
PK	pharmacokinetic
PO	oral(ly)
PR	partial response
PT	preferred term
Q1	first quartile
Q3	third quartile
QD	daily
RECIST	Response Evaluation Criteria in Solid Tumors
Rp	BRLF1 promoter
RT-PCR	real time-polymerase chain reaction
SAE	serious adverse event
SAP	Statistical Analysis Plan
SD	stable disease
SI	International System of Units
SMQ	Standardized MedDRA Query
SOC	system organ class
STDEV	standard deviation
TEAE	treatment-emergent adverse event
TIL	tumor infiltrating lymphocyte
Tmax	time to Cmax

WHO World Health Organization

## Zp BZLF1 promoter

Zta EBV lytic protein

## **2. INTRODUCTION**

This statistical analysis plan (SAP) describes the analyses and data presentations for Celgene's protocol CC-486-NPC-001 "A Phase 2, Multicenter, International, Single Arm Study to Assess the Safety and Efficacy of Single Agent CC-486 (Oral Azacitidine) in Previously Treated Subjects with Locally Advanced or Metastatic Nasopharyngeal Carcinoma", which was finalized on 11 July 2014 and subsequently amended on 1 October 2014 (Amendment 1), 03 April 2015 (Amendment 2), and 23 September 2016 (Amendment 3). It contains definitions of analysis populations, derived variables and statistical methods for the analysis of efficacy and safety.

These analyses include one pre-planned interim analysis, and a final analysis. The purpose of the SAP is to ensure the credibility of the study findings by pre-specifying the statistical approaches to any data analysis prior to database lock. This SAP will be finalized and signed prior to the clinical database lock for the final analysis. All statistical analyses detailed in this SAP will be conducted using SAS® Version 9.2 or higher.

CELGENE PROPRIETARY INFORMATION

### **3. STUDY OBJECTIVES**

#### **3.1. Primary Objective**

The primary objective is to evaluate the efficacy of CC-486 in subjects with nasopharyngeal carcinoma (NPC).

#### **3.2. Secondary Objectives**

The secondary objectives are to evaluate safety in all subjects and pharmacokinetics (PK) of CC-486 in a subset of subjects of Asian-Pacific Island ethnicity at experienced selected sites.

#### **3.3. Exploratory Objectives**

[REDACTED]

## 4. INVESTIGATIONAL PLAN

### 4.1. Overall Study Design and Plan

This is a Phase 2, single arm, multicenter, international study to assess the safety and efficacy of single agent CC-486 (oral azacitidine) in previously treated subjects with locally advanced or metastatic NPC, who have progressed (clinically or radiographically) after having received 1 or 2 previous regimens, including a platinum-based chemotherapy. The primary endpoints are overall response rate (ORR) and progression-free survival (PFS).

Approximately 51 to 55 efficacy evaluable subjects will be enrolled according to Simon's optimal two-stage design; if the predefined activity is met (> 4 responses [complete response (CR)/partial response (PR)] out of the first 17 efficacy evaluable subjects based on independent radiological assessment), then the study will continue to enroll an additional 34 efficacy evaluable subjects. If  $\leq$  4 responses out of 17 are observed, then the study enrollment will be stopped. The Stage 1 decision will be based on ORR only, and the Stage 2 decision will be based on both ORR and PFS. Subjects who are not evaluable for efficacy will be replaced at the discretion of the sponsor. Subjects who are discontinued from study prior to the first tumor assessment for any reason other than for progressive disease are not evaluable and will be replaced. Subjects who progress prior to the end of Cycle 1 are not evaluable and will be replaced.

The study will consist of the following visits:

**Screening Assessments:** Screening evaluations will be performed for all subjects to determine study eligibility. These evaluations must be completed within 21 days of first dosing unless otherwise noted.

**Treatment:** Subjects meeting eligibility criteria must start treatment within 21 days of signing the informed consent form (ICF). For all subsequent visits, an administrative window of  $\pm$  2 days is permitted. Treatment cycles are 21 days in duration. All evaluations should be performed prior to dosing on the visit day, unless otherwise specified. CC-486 will be administered at a dose of 300 mg orally (PO) daily (QD) on Days 1 to 14 of a 21-day cycle. However, the first 6 subjects of Asian-Pacific Island ethnicity evaluable for safety will receive CC-486 at a dose of 200 mg orally QD on Days 1 to 14 of 21 days of Cycle 1; and if well-tolerated, and there are no safety concerns, subsequent subjects of Asian-Pacific Island ethnicity will be treated at the 300 mg QD on Days 1 to 14 of a 21-day cycle.

**Response Assessment by Response Evaluation Criteria In Solid Tumors (RECIST) v 1.1:** Response assessments (tumor evaluations) should be performed at screening within 28 days before the start of investigational product (IP), and every 6 weeks ( $\pm$  5 days) from Cycle 1 Day 1 (C1D1) for the first 3 tumor evaluations and then every 9 weeks until disease progression, start of a new anticancer therapy, or withdrawal of consent from the entire study. Evaluation of response will be performed using RECIST v1.1.

An independent radiological assessment of responses will be conducted using RECIST v1.1.

Response assessments include computed tomography (CT) scan or magnetic resonance imaging (MRI) of the head and neck with supraclavicular node imaging, the chest and abdomen/pelvis,

neurological examination with facial nerve evaluation, and bone scans at baseline for all subjects. Bone scans will be repeated only if the subject is symptomatic or with known bone metastasis. The same mode of imaging for lesion evaluation at screening must be used consistently throughout the study.

All subjects with evidence of objective tumor response (CR or PR) should have the response confirmed with repeat assessments at the next scheduled scan, but after no less than 4 weeks. Response assessments must have occurred  $\geq$  6 weeks from Cycle 1 Day 1 to be considered as SD for a best response.

**End of Treatment (EOT) Evaluation:** An EOT evaluation should be performed for subjects who are withdrawn from treatment for any reason as soon as possible after the decision to permanently discontinue treatment has been made. Radiologic response assessment will be repeated only if required per the defined study imaging schedule.

**Adverse Event (AE) Collection and Follow-up:** Any AE that started after signing ICF and up to 28 days after the last dose of IP and those serious AEs (SAEs) made known to the Investigator at any time thereafter that are suspected of being related to IP will be collected.

**Follow-up for Efficacy Endpoints:** All subjects who discontinue treatment for reasons other than disease progression, start of new anticancer therapy, or withdrawal of consent from the entire study will be followed for tumor response assessments and subsequent anticancer therapies.

**Follow-up for Survival:** After the EOT visit, all subjects will be followed every 8 weeks ( $\pm$  5 days) for survival until withdrawal of consent, death, or lost-to-follow up, whichever occurs first. Subsequent anticancer therapies should be collected at the same schedule. New anticancer therapy includes (but is not limited to) any systemic or local medication, surgery, radiation, or any other therapy intended to treat the subject's cancer.

Survival follow-up may be conducted by record review (including public records) and/or telephone contact with the subject, family, or the subject's treating physician.

**Pharmacokinetics:** A subset of enrolled subjects (Asian-Pacific island ethnicity only) at a selected number of experienced sites that have the ability to collect, process, and ship CC-486 PK samples will participate in PK sample collection. Six subjects of Asian-Pacific island ethnicity initially being administered 200 mg CC-486 on Days 1 to 14 of a 21-day cycle will be asked to participate in the PK sample collection at these selected sites. An additional 6 subjects of Asian-Pacific ethnicity will participate in the PK sampling if the dose is escalated to 300 mg in this population.

On each PK day (ie, Cycle 1 Days 1 and 14), subjects will ingest IP in the clinic after performing the required overnight fasting, if applicable taking antiemetic premedication (eg, odansetron), and completing the required pre-dose assessments (where applicable), with each dose being given at approximately the same time of day.

Blood samples for oral azacitidine PK assessment will be collected prior to each dose administration (pre-dose) and over the 8-hour period following each dose administration (0.25, 0.5, 1, 1.5, 2, 2.5, 3, 3.5, 4, 6, and 8 hours post-dose or similar schedule).

**Biomarkers:** Biomarkers will be assessed for Stage 1 subjects only.

#### **4.1.1. Primary Endpoints**

The primary endpoints are:

- ORR defined as the combined incidence of CR and PR, confirmed no less than 4 weeks after the criteria for response are first met, based on independent radiology assessment using RECIST v1.1, AND
- PFS measured as time from the start of the study treatment to progression, based on an independent radiology assessment of response using RECIST v1.1 or death (from any cause), whichever is earlier.

#### **4.1.2. Secondary Endpoints**

The secondary endpoints include:

- Overall survival (OS) defined as the time from first treatment to death by any cause.
- Disease control rate (DCR) defined as the combined incidence of CR and PR, confirmed no less than 4 weeks after the criteria for response are first met, and stable disease (SD) for  $\geq 16$  weeks from the date of first treatment, based on independent radiology assessment using RECIST v1.1.
- Safety to include the incidence of treatment-emergent AEs (TEAEs), SAEs, Grade 3-4 AEs, Grade 3 and higher AEs, AEs of special interest, and laboratory abnormalities and other safety parameters.
- PK of CC-486 in a subset of subjects of Asian-Pacific Island ethnicity at experienced selected sites.

#### **4.1.3. Exploratory Endpoints**

### **4.2. Stratification, Randomization and Blinding**

Not applicable for this study.

### **4.3. Sample Size Determination**

The sample size estimation is based on having sufficient sample in the Efficacy Evaluable Population (see [Section 5.2.3](#)) to show that the ORR is higher than 20% or median PFS is  $> 5$  months. Simon's optimal two-stage design will be used (Simon, 1989). The null hypothesis that the true ORR is  $\leq 20\%$  or median PFS is  $\leq 5$  months will be tested against a one-sided alternative. In the first stage, 17 subjects will be accrued. If there are  $\leq 4$  responders among these 17 subjects, enrollment will be stopped. Otherwise, if there are  $> 4$  responders, 34 additional

subjects will be accrued for a total of 51 subjects. Subjects who progress by the end of Cycle 1 are not evaluable for efficacy and will be replaced. This Phase 2 study will be considered positive if more than 14 responders are observed in 51 subjects or the hypothesis of median PFS  $\leq$  5 months (alternatively, the PFS rate at 5 months is  $\leq$  50%) is rejected. This design yields a marginal one-sided type I error rate of 5% and power of 85% when the true ORR is 40%. After the second stage ( $n = 51$  subjects), the power for showing a median PFS of  $> 5$  months is 80% (60%) when the true median PFS is about 8 (7) months.

CELGENE PROPRIETARY INFORMATION

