### 10.1. Multiplicity

There is no multiplicity adjustment for the efficacy endpoints.

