### 10.2. Analysis of the Efficacy Endpoints

The primary efficacy endpoints are ORR and PFS.

Overall response rate is defined as the combined incidence of CR and PR, confirmed no less than 4 weeks after the criteria for response are first met, based on independent radiology assessment using RECIST version 1.1. After the enrollment of 51 patients, if more than 14 responders are observed, the null hypothesis ( $ORR \leq 20\%$ ) will be rejected, the true ORR will be concluded to be  $> 20\%$ . The point estimate and two-sided 90% CI of ORR will be provided using the Clopper-Pearson method (Clopper, 1934).

Progression-free survival will be based on independent radiology assessed response using RECIST v1.1. Progression-free survival is defined as the time from the date of start of the study treatment to the date of disease progression or death (any cause) on or prior to the data cut-off date for the statistical analysis, whichever occurs earlier. Subjects who do not have disease progression or have not died as of the data cut-off date will be censored at the time of the last radiologic assessment prior to the data cut-off date. In the event that a new anticancer therapy is initiated for a subject prior to documented progression, the subject will be censored at the time of the last radiologic assessment where the subject was documented to be progression-free prior to the initiation of the new anticancer therapy. Subjects with a single missing radiologic assessment prior to a visit with documented disease progression (or death) will be analyzed as a PFS event at the time of the radiologic assessment that shows progression (or death). Subjects with  $\geq 2$  consecutive missing radiologic assessments prior to a visit with documented disease progression (or death) will be censored at the time of the last radiologic assessment where the subject was documented to be progression-free prior to the first of the  $\geq 2$  consecutive missing visits.

The Kaplan-Meier (K-M) method will be used to estimate PFS distribution, and the medians with two-sided 90% CIs will be reported. Since the study did not enter the second stage, no hypothesis testing will be conducted for PFS. The K-M estimates of PFS rates at each 2-month interval will be provided. Kaplan-Meier curves for PFS will be presented.

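### Does the stated PFS power of 80% (60%) with 51 subjects fail at a one-sided 5% level?

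*SAP*

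**What the plan says.** Section 4.3 of the SAP sets a null hypothesis for PFS of a median of at most 5 months, which "will be tested against a one-sided alternative". The sentence that defines a positive study adds a second form in brackets: "alternatively, the PFS rate at 5 months is" at most 50%. If Stage 1 is passed, 34 more "subjects will be accrued for a total of 51 subjects".

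Two sentences then give operating characteristics. The one on response reads "This design yields a marginal one-sided type I error rate of 5% and power of 85% when the true ORR is 40" percent. The one on PFS applies after the second stage, with 51 subjects, and says that the power for showing a median above 5 "months is 80% (60%) when the true median PFS is about 8 (7) months".

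Section 10.1 says: "There is no multiplicity adjustment for the efficacy endpoints". Section 10.2 specifies Kaplan-Meier estimation of PFS, and "the medians with two-sided 90% CIs will be reported". It also states that, because the second stage was not entered, PFS will not be tested. The SAP gives no PFS test statistic, distribution, event count or follow-up time.

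**The concern.** The bracketed rate form is the only version of the PFS hypothesis that can be turned into a test without further inputs: count the subjects progression-free at 5 months and compare with one half. The only error rate in Section 4.3 is one-sided 5%, and two-sided 90% intervals agree with it. On that reading, with exponential PFS, 51 subjects give about 68% (46%). At one-sided 10% a normal approximation gives 81.0% (61.4%), very near the printed pair, so it is tempting to infer that a 10% calculation was placed beside a 5% claim.

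If that were so, one of the two primary endpoints, either of which can make the study positive, would have less power or twice the type I error that the section conveys.

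**Working it through.** **Inputs.** From Section 4.3: n = 51; null median 5 months; alternatives 8 and 7 months; one-sided test. The 5% level stands in the response sentence and is taken to apply to PFS as well. Not in the SAP, and assumed unless said otherwise: exponential PFS and no censoring before 5 months.

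**Check on the neighbouring response figures.** Continuing with more than 4 responders in 17, and declaring success with more than 14 in 51, gives a type I error of 4.87% at a true ORR of 20% and power of 85.4% at 40%. Both agree with the SAP.

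**1. Test of the median at one-sided 5%.** For exponential data the large-sample standard error of the sample median is SE(m) = m / (ln 2 × √n).
- SE(5) = 5 / (0.6931 × 7.141) = 1.010 months.
- Critical value: 5 + 1.645 × 1.010 = 6.66 months.
- SE(8) = 1.616; power = Φ((8 − 6.66) / 1.616) = Φ(0.828) = 79.6%.
- SE(7) = 1.414; power = Φ((7 − 6.66) / 1.414) = Φ(0.239) = 59.5%.

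Both printed figures are reproduced, with no 10% level involved.

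**2. Exact exponential test at one-sided 5% with d events.** Power = P(χ²[2d] > c × 5/m), where c is the 95th percentile of χ²[2d].
- d = 28: c = 74.47; power 81.2% (58.2%).
- d = 29: c = 76.78; power 82.3% (59.3%).

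These are within about 2.5 points of the printed pair.

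**3. The 5-month rate against 50% at one-sided 5%.** Under the exponential, S(5) = exp(−ln 2 × 5/m), which is 0.648 for a median of 8 and 0.610 for 7.
- Exact binomial: reject at 32 or more of 51 (size 4.6%); power 68.1% (45.7%).
- Normal approximation with null variance: 69.1% (46.7%).

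This is the calculation behind the doubt, and it is correct for that test and that distribution.

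**4. The same rule (32 or more of 51) with another distribution.** For a Weibull with the same medians, S(5) = exp(−ln 2 × (5/m)^k).

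| Shape k | S(5), median 8 (7) | Power, median 8 (7) |
|---|---|---|
| 1.0 (exponential) | 0.648 (0.610) | 68.1% (45.7%) |
| 1.1 | 0.661 (0.620) | 74.8% (51.6%) |
| 1.2 | 0.674 (0.629) | 80.6% (57.4%) |
| 1.25 | 0.680 (0.634) | 83.2% (60.2%) |

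A mildly rising hazard brings the rate test itself to roughly 80% (60%) at one-sided 5%. The shortfall in step 3 is therefore a property of the assumed shape. The exponential has no special standing here, since Section 4.3 also replaces subjects who progress by the end of Cycle 1.

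**5. The supposed 10% level.** The normal approximation for the rate test gives 81.0% (61.4%). The exact rule at 10% (31 or more of 51, size 8.0%) gives 77.6% (57.1%). The 10% explanation thus fits only by approximation, and no better than the one-sided 5% test of the median in step 1.

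**The case for a change.** The strongest reply is that steps 1 and 2 use ingredients the SAP does not contain. The normal test of the median is only approximate: with its cut-off of 6.66 months, the actual type I error at n = 51 is 6.8%. If the cut-off is moved to 6.85 months so that the size is exactly 5%, the power is 77.5% (54.3%). The exponential test needs an event count, and with all 51 events it would give about 95% (79%). By contrast, deciding by the lower 90% Kaplan-Meier limit for the median (linear or log-log, complete follow-up to 5 months) is the same rule as 32 or more of 51. Under exponential PFS it gives 68.1% (45.7%), and reaching 80% (60%) would need true medians of about 8.7 (7.6) months.

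Those numbers are right, and part of the point stands. The median and rate forms are presented as interchangeable although their power can differ, and a reader cannot tell which calculation produced the figure. But the reply also relies on an ingredient that is absent from the SAP, namely the exponential distribution, without which 68% (46%) does not follow. That the basis is unstated does not show the number to be wrong, and design-stage power is commonly computed with large-sample formulas.

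It could also be said that the figure ignores the chance of stopping at Stage 1 on response alone. The sentence already confines itself to the situation after the second stage, so that condition is disclosed.

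**Conclusion.** The concern does not hold. The power sentence is about the median, and a standard large-sample test of the median at nominal one-sided 5% with 51 subjects returns 79.6% (59.5%) against the stated 80% (60%). The lower figure of 68.1% (45.7%) belongs to the bracketed rate form, or an equivalent Kaplan-Meier limit, under exponential PFS. With a Weibull shape of 1.2 the same rule gives 80.6% (57.4%). Nothing in the SAP supports an undeclared 10% level. Replacing the printed pair with 68% (46%) would tie the SAP to one test and one distribution that it does not specify.

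The conclusion rests on reading the 5% level as applying to PFS and, for steps 1 to 3, on exponential PFS. Step 1 is an approximation whose true size is somewhat above 5%. The remaining gap, that the test, distribution and event count are not named, is one of reporting detail. It affects no result, because Section 10.2 rules out any PFS hypothesis test now that Stage 2 was not entered.

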## 5. GENERAL STATISTICAL CONSIDERATIONS

### 5.1. Reporting Conventions

- All tables will be presented by ‘AP 200 mg’, ‘300 mg’, and ‘Total’, unless otherwise specified.
- Data from all study centers will be combined for analysis.
- P-values will be rounded to 4 decimal places. P-values that round to 0.0000 will be presented as ‘< 0.0001’ and p-values that round to 1.000 will be presented as ‘> 0.9999’.
- Confidence intervals (CIs) will be presented as 2-sided 90% CIs unless specified differently in specific analyses.
- Summary statistics will consist of the number and percentage of subjects (or cycles, if appropriate) in each category for discrete variables, and the sample size, mean, median, standard deviation (STDEV), first and third quartiles, minimum and maximum for continuous variables.
- All mean and quartile values will be formatted to one more decimal place than the measured value. Standard deviation values will be formatted to 2 more decimal places than the measured value.
- All percentages will be rounded to 1 decimal point. The number and percentage of responses will be presented in the form XX (XX.X), where the percentage is in the parentheses.
- All analysis and summary tables will have the analysis population sample size (ie, number of subjects) in the column heading.
- All listings will be sorted for presentation in order of study site, subject identification and date of procedure or event.
- The day of the first dose of study drug will be defined as Day 1.
- Each cycle starts with the date of the first dose date of the cycle, and the last day of the cycle is the day before the first dose date of the subsequent cycle; The cycle number for each date of interest, eg, AE, will be calculated based on the cycle window set by its start and end dates. If a date is on or after start date of cycle i and before start date of cycle (i+1), the corresponding cycle number will be “i”.
- For the last cycle, the last day of the cycle is the treatment discontinuation date on the case report form (CRF) EOT page or the Day 1 of the last cycle + 20, whichever is earlier.
- In by-cycle analyses, assessments taken pre-dose on Day 1 of a given cycle (eg, laboratory measures) will be grouped with the previous cycle.

- Baseline value will be defined as the last non-missing value before the first dose of study drug is administered; for subjects who were not treated, the baseline will be the assessment value taken on the Screening visit.
- Partial dates will be imputed based on the rules specified in Section 18.3.
- All laboratory data will be reported using International System of Units (SI).
- Summaries of the most severe toxicity grade in clinical laboratory in each treatment cycle and most severe grade post-baseline overall and shifts from baseline to most severe toxicity grade post-baseline overall will include all scheduled and unscheduled assessments. A similar approach will be used for summaries of Eastern Cooperative Oncology Group (ECOG) performance status.
- For safety parameters, the Final Evaluation will be defined as the last on-treatment value, which is the last non-missing assessment on or prior to the last dose date + 28 days or the treatment discontinuation date, whichever is later.
- SAS® Version 9.2 (or higher) will be the statistical software package used to produce all data summaries, listings, graphs, and statistical analyses.

